8. VITAL SIGNS OUTPUT SPECIFICATIONS

During treatment visits, vital signs (temperature, pulse and BP) are measured immediately prior to the infusion, then every 15 minutes during the infusion until one hour, followed by every 30 minutes until the end of the infusion; a further reading is taken at least one hour after completion of the infusion. These data will be summarized within each visit by planned assessment time-point and also as changes from the within-visit pre-infusion value.

Additionally, vital signs plus height and weight will be summarized descriptively by visit (using pre-infusion values when appropriate), including changes from the baseline pre-infusion value.

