4. BASELINE DEMOGRAPHICS AND BASELINE INFORMATION

Descriptive summaries of the following information will be produced to characterize baseline characteristics for the safety population:

- Demographic characteristics, including:
 - age, both as descriptive summary and as counts and percentages falling into the following categories:
 - 2 – 11 years
 - 12 – 17 years
 - sex
 - race
 - ethnicity
 - height
 - weight
 - body surface area
- Baseline disease characteristics:
 - GPA or MPA disease
 - ANCA result (C-ANCA, P-ANCA, Negative)
 - Duration of disease
 - Pediatric Vasculitis Damage Index (PVDI)
- Previous and current treatment for GPA or MPA
 - A glossary showing the mapping of investigator verbatim terms to coded medications will be produced also
- Immunization history
- Patients' medical history, grouped by preferred term within SOC
 - A glossary showing the mapping of investigator verbatim terms to coded diseases will be produced also
- Alcohol, tobacco and substance use
- Female reproductive status

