Native Hawaiian or other Pacific Islander	nn (xx.x%)
White	nn (xx.x%)
Multiple	nn (xx.x%)
Other	nn (xx.x%)
Unknown	nn (xx.x%)
Height (cm) ASL.BWT	
n	nnn
Mean (SD)	xx.x (xx.x)
Median	xx.x
Q1 – Q3 (IQR)	xx.x – xx.x (xx.x)
Min–Max	xx–xx

	Rituximab (N=nnn)
Weight (kg) ASL.BWT	
n	nn
Mean (SD)	xx.x (xx.x)
Median	xx.x
Q1 – Q3 (IQR)	xx.x – xx.x (xx.x)
Min–Max	xx–xx
Body-mass index (kg/m2) ASL.BBMI	
n	nn
Mean (SD)	xx.x (xx.x)
Median	xx.x
Q1 – Q3 (IQR)	xx.x – xx.x (xx.x)
Min–Max	xx–xx
Concomitant Diseases (continuing at Baseline)	
n	nn
No concomitant diseases	nn (xx.x%)
1 concomitant disease	nn (xx.x%)
2 concomitant diseases	nn (xx.x%)
>=3 concomitant diseases	nn (xx.x%)
Smoking history	
n	nn
Current	nn (xx.x%)
Previous	nn (xx.x%)
Never	nn (xx.x%)
Alcohol history	
n	nn
Current	nn (xx.x%)
Previous	nn (xx.x%)
Never	nn (xx.x%)

Estimated GFR (Schwartz formula) (mL/min/1.73 m2)	
n	nn
Mean (SD)	xx.x (xx.x)
Median	xx.x
Q1 – Q3 (IQR)	xx.x – xx.x (xx.x)
Min–Max	xx.x–xx.x
immunofluorescence (IF) ANCA status	
Negative	nn (xx.x%)
cANCA	nn (xx.x%)
pANCA	nn (xx.x%)
MPO	nn (xx.x%)
PR3	nn (xx.x%)
BVAS/WG Score	
n	nn
Mean (SD)	xx.x (xx.x)
Median	xx.x
Q1 – Q3 (IQR)	xx.x – xx.x (xx.x)
Min–Max	xx.x–xx.x

Current Disease Status

n	
Severe Flare/New Disease	nn (xx.x%)
Limited Flare/New Disease	nn (xx.x%)
Persistent Severe Disease	nn (xx.x%)
Persistent Limited Disease	nn (xx.x%)
Remission	nn (xx.x%)

BVAS/WG PGA

n	nn
Mean (SD)	xx.x (xx.x)
Median	xx.x
Q1 – Q3 (IQR)	xx.x – xx.x (xx.x)
Min–Max	xx.x–xx.x

PVAS Score

n	nn
Mean (SD)	xx.x (xx.x)
Median	xx.x
Q1 – Q3 (IQR)	xx.x – xx.x (xx.x)
Min–Max	xx.x–xx.x

PVDI Score

n	nn
Mean (SD)	xx.x (xx.x)
Median	xx.x
Q1 – Q3 (IQR)	xx.x – xx.x (xx.x)
Min–Max	xx.x–xx.x

[figure not shown]
PVDI Average School Absence (days)

[figure not shown]
n	nn
=<1	nn (xx.x%)
>1 - 4	nn (xx.x%)
>4 - 10	nn (xx.x%)
>10	nn (xx.x%)

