
ID: EX001.1SP
 
Summary of Rituximab Exposure
	
STREAM Template: None
 
Analysis Population: Safety Evaluable Population
 
Analysis Variables: See mock. Percentages are based on n. Include data from Day 1 to common closeout date.
 
- study end date =
 
 1. For early discontinuation or completion patients: minimum of or early withdrawal/discontinuation or patient completed study 2. For the rest of patients: minimum of common closeout date and last known alive date 
Duration of observation = study end date – study start date + 1.
 
Date of last contact is the last available date of efficacy, complete medication start date, laboratory, adverse event assessments, early withdrawal visit, date of last contact or date of death.

---	---

Total number of Infusions administered	
n	nn
Mean (SD)	xxx.x (xx.x)
Median	xx.x
Q1-Q3 (IQR)	xx.x-xx.x (xx.x)
Min - Max	xx - xxx
Total cumulative dose (mg)	
n	nn
Mean (SD)	xxx.x (xx.x)
Median	xx.x
Q1-Q3 (IQR)	xx.x-xx.x (xx.x)
Min - Max	xx - xxx
Duration of Observation (Months)	
n	nn
Mean (SD)	xx.x (xx.x)
Median	xx.x
Q1-Q3 (IQR)	xx.x-xx.x (xx.x)
Min - Max	xx.x - xx.x
Duration of Observation (Months)	
n	nn
Duration ≤ 6	nn (xx.x%)
6 < Duration ≤ 12	nn (xx.x%)
12 < Duration ≤ 18	nn (xx.x%)
18 < Duration ≤ 24	nn (xx.x%)
24 < Duration ≤ 36	nn (xx.x%)
36 < Duration ≤ 48	nn (xx.x%)
48 < Duration ≤ 60	nn (xx.x%)
Duration > 60	nn (xx.x%)
Total patient years of observation	xxx.xx

ID: EX001.2SP

STREAM Template: None

Rituximab
Administration over
Course of study

[figure not shown]
Analysis Population: Safety Evaluable Population

Plot of:

Y-Axis: Patient ID

X-Axis: Study Visit

See mockup.

ID: EX002SP

Listing of Rituximab Administrations, Interruptions and Modifications

STREAM Template: None

Analysis Population: Safety Evaluable Population

Column Variables: Include data from Day 1 to common closout date.

Add "Dose Administered" column in "mg/m²" calculating as follows:

administered dose (mg/m²) = dose administered (mg) / BSA (m²),

where

$$BSA = \text{body surface area} = \text{sqrt} [BW \times Ht / 3600]$$

BW = weight (kg)

Ht = height (cm)

See mockup

Sorting: Sort by center / patient ID and treatment administration day.

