8.1 Vital Signs Output Specifications

ID: VS001SP
 
Vital Sign Results and Change from Pre-infusion by Infusion Number in Remission Induction Phase
	
STREAM Template: VST01
 
Analysis Population: Safety Evaluable Population
 
Column Variables: Value after infusion and Change from Pre-infusion.
 
Analysis Variables: Separate tables in one file for each of: pulse rate (display as “heart rate” in the output), systolic blood pressure, and diastolic blood pressure. Use pre-infusion values only.
 
Include planned infusions (in the remission induction phase).
 
Statistics and Calculation Methods: Time-points to include are: pre-infusion and 0.25, 0.5, 0.75, 1, 1.5, 2, ... 6 hours post-infusion.
 
Numeric Precision and Formatting of Statistics: See mockup

---	--

Time-point Relative to Infusion Start		Value at Time-point	Change from Pre-infusion
Infusion 1			
Pre-infusion	n	nn	
	Mean (SD)	xxx.x (xx.x)	
	Median	xxx.x	
	Q1 – Q3 (IQR)	xx.x-xx.x(xx.x)	
	Min-Max	xxx.x-xxx.x	
0.25 hours Post	n	nn	nn
	Mean (SD)	xxx.x (xx.x)	xxx.x (xx.x)
	Median	xxx.x	xxx.x
	Q1 – Q3 (IQR)	xx.x-xx.x(xx.x)	xx.x-xx.x(xx.x)
	Min-Max	xxx.x-xxx.x	xxx.x-xxx.x
Infusion 2 ...			

ID: VS002SP
 
Vital Sign Results and Change from Baseline by Visit
	
STREAM Template: VST01
 
Analysis Population: Safety Evaluable Population
 
Column Variables: Value at visit and Change from Baseline.
 
Statistics and Calculation Methods: Analysis visits to include are: Baseline, Weeks 1 to 3, Months 1, 2, 4, 6, 9, 12, 15 and 18.
 
Values at visits to include only patients for whom a baseline value is included.
 
Numeric Precision and Formatting of Statistics: See mockup

--	--

Visit		Value at Visit	Change from Baseline
Day 1 (Baseline)	n	nn	
	Mean (SD)	xxx.x (xx.x)	
	Median	xxx.x	
	Q1 – Q3 (IQR)	xx.x-xx.x(xx.x)	
	Min-Max	xxx.x-xxx.x	
Week 1	n	nn	nn
	Mean (SD)	xxx.x (xx.x)	xxx.x (xx.x)
	Median	xxx.x	xxx.x
	Q1 – Q3 (IQR)	xx.x-xx.x(xx.x)	xx.x-xx.x(xx.x)
	Min-Max	xxx.x-xxx.x	xxx.x-xxx.x
Week 2	n	nn	nn
	Mean (SD)	xxx.x (xx.x)	xxx.x (xx.x)
	Median	xxx.x	xxx.x
	Q1 – Q3 (IQR)	xx.x-xx.x(xx.x)	xx.x-xx.x(xx.x)
	Min-Max	xxx.x-xxx.x	xxx.x-xxx.x
...			

ID: VS003SP Vital Sign Results and Changes from Baseline Above and Below Specified Limits by Visit	STREAM Template: None				
	Analysis Population: Safety Evaluable Population				

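### Height and weight are planned only as raw change pooled over ages 2 to under 18, which cannot separate altered growth from normal growth

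*SAP*

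**What the plan says.** SAP Section 8 states that "vital signs plus height and weight will be summarized descriptively by visit", "including changes from the baseline pre-infusion value". Output VS002SP in Section 8.1 is the matching shell. It shows the value at each visit and the change from baseline as mean (SD), median, quartiles and range. It has no line naming its variables, so height and weight are not mentioned. Its visit list reads "Analysis visits to include are: Baseline, Weeks 1 to 3, Months 1, 2, 4, 6, 9, 12, 15 and 18".

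The schedule (Protocol Appendix 1, SAP Appendix 2) has height and weight at screening, at baseline and from Month 1 onward, but not at Weeks 1 to 3. The visible SAP contains no standard deviation score, percentile, growth velocity or growth reference.

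For the baseline description, the list in SAP Section 4 includes "body surface area". Table DM001SP in Section 4.3 has the rows "Height (cm) ASL.BWT", "Weight (kg) ASL.BWT" and "Body-mass index (kg/m2) ASL.BBMI", and no body surface area row.

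**The concern.** A raw change in centimetres or kilograms means different things at different ages. A young child gains height in 18 months whatever the treatment does, and a 17-year-old may gain almost none. With both in one summary, the average depends heavily on who was enrolled.

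Three features of this trial leave nothing to correct for that. There is no control arm to show normal growth, subgroup summaries are excluded, and no external reference is named.

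The question is a reasonable one here. Safety and tolerability is a primary objective. All patients start oral glucocorticoid at up to 1 mg/kg/day, tapered by Month 6 (Protocol 4.3.2.3.1). The schedule keeps oral glucocorticoids on the visit grid afterwards, and the duration categories in SAP Section 5.1 run to three years and more. The sites collect serial height and weight, so what is at stake is whether the planned table lets anyone interpret them.

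**Working it through.** The plan gives no growth figure to reproduce, so the check has two parts: an illustration of the size of the problem, and a comparison of the texts.

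**1. Raw gain by age.** Inputs from the documents: ages 2 to under 18 (Protocol 4.1.1), 25 patients planned, Month 18 on Day 545. The growth rates are assumptions: 5 to 7 cm/year in mid-childhood and 0 to 1 cm/year at 16 to 17 years.

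Expected gain = rate × 1.5 years.
- Mid-childhood: 1.5 × 5 = 7.5 cm to 1.5 × 7 = 10.5 cm.
- Late adolescence: 1.5 × 0 = 0 cm to 1.5 × 1 = 1.5 cm.

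The two groups differ by 7.5 − 1.5 = 6.0 cm to 10.5 − 0 = 10.5 cm. Moving 5 of 25 patients (20%) from one group to the other shifts the pooled mean by 0.2 × 6.0 = 1.2 cm to 0.2 × 10.5 = 2.1 cm with no treatment effect. That is as large as an assumed deficit of 1 to 2 cm.

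**2. The same mean from different causes.** Exact follow-up is (545 − 1)/365.25 = 1.49 years.
- 6 cm/year with no slowing: 6 × 1.49 = 8.9 cm.
- 8 cm/year with 25% slowing: 8 × 1.49 × 0.75 = 8.9 cm.
- 6 cm/year, with 40% of patients no longer growing and no slowing: 0.6 × 8.9 = 5.4 cm. A uniform 40% slowing at 6 cm/year gives the same figure.

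**3. A large effect.** With 50% slowing, the loss is 3.0 cm at 4 cm/year (6.0 to 3.0) and about 4.5 cm at 6 cm/year (8.9 to 4.5). A loss of that size exceeds the 1.2 to 2.1 cm shift in step 1, so it might be noticed even on the raw scale.

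**4. Does the DM001SP error reach the growth analysis?** No. VS002SP takes change from the baseline defined in SAP 3.2.1, the last pre-treatment value. DM001SP only describes the population. The dose is calculated from height and weight measured in the 28 days before baseline (Protocol 4.3.2.1.1), not from this table.

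**5. Body surface area formula.** Protocol 4.3.2.1.1 uses the Dubois formula, weight^0.425 × height^0.725 × 0.00718. Listing EX002SP in SAP 5.1 uses √(weight × height/3600). For assumed body sizes:

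| Weight, height | Protocol formula (m²) | EX002SP formula (m²) | 375 mg/m² by protocol formula, as EX002SP would list it |
|---|---|---|---|
| 12 kg, 86 cm | 0.522 | 0.535 | 365.3 mg/m² |
| 30 kg, 135 cm | 1.068 | 1.061 | 377.4 mg/m² |
| 60 kg, 168 cm | 1.680 | 1.673 | 376.4 mg/m² |

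The last column was computed before rounding. The differences are small and vary with body size.

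**The case against.** The strongest reply is that growth is not a visible objective or endpoint. The primary safety outcomes are adverse events and laboratory abnormalities. Glucocorticoid is background therapy, and no hypothesis is tested. The documents do not list slowed growth or weight gain as an expected harm. Even a standardised score, in one arm, could not divide a change between rituximab, steroid and disease. All of this stands, and it makes the scores an inexpensive improvement to a descriptive safety summary rather than the repair of a failed analysis.

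Other routes may also exist. New or worsened examination findings are recorded as adverse events (Protocol 4.5.3.4). The efficacy and pharmacodynamic sections are largely redacted, so a growth measure there can be neither asserted nor excluded. VS002SP shows quartiles and range as well as the mean. That display of spread helps little, because it does not tie a change to the child's age or sex.

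A reader might go further and infer that growth effects cannot be read from this trial at all, or that the DM001SP errors contribute to that. The documents support neither reading. Age, sex and serial measurements are collected, so scores can still be derived; only the planned summary lacks them. The shared ASL.BWT annotation looks like a copying slip under a correctly labelled row. Body surface area is missing from that table but not from the plan, since SAP Section 4 lists it and EX002SP uses it. Nor is it supported that the pooled mean hides any effect whatever, as step 3 of the working shows.

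**Conclusion.** The point holds in a limited form. The height and weight summary in SAP Section 8 cannot distinguish altered growth or weight gain from normal age- and sex-driven change. On the assumed growth rates, a height deficit of about 1 to 2 cm over 18 months would be hidden by the age mix, while a much larger one might not be. Those rates and the deficit are assumptions; the structural argument rests only on the age range, the single arm, the absence of subgroups and the raw scale. The same reasoning applies to weight, for which no figure is offered.

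The height annotation and missing row in DM001SP are a separate, minor correction to a table shell. They affect the description of the population and nothing downstream. The two body surface area formulas are an inconsistency between the documents that must be reconciled.

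**What to change.** **Growth summary.** Name height and weight as analysis variables in VS002SP, at the visits where they are scheduled (baseline and Month 1 onward). Add age- and sex-specific standard deviation scores for height, weight and BMI, with change from baseline at Months 6, 12 and 18 beside the raw values. Name one growth reference before database lock. State that the result is descriptive and does not attribute cause.

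**Table shell.** In DM001SP, map the height row to the baseline height variable and add the body surface area row that SAP Section 4 already lists. State one body surface area formula for the analysis outputs, and reconcile Protocol 4.3.2.1.1 with EX002SP.

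**Cost.** A published reference table and some programming, with no new visits or measurements. The drawback is that one reference is only approximate across eight countries.

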8.1 Vital Signs Output Specifications

ID: VS001SP
 
Vital Sign Results and Change from Pre-infusion by Infusion Number in Remission Induction Phase
	
STREAM Template: VST01
 
Analysis Population: Safety Evaluable Population
 
Column Variables: Value after infusion and Change from Pre-infusion.
 
Analysis Variables: Separate tables in one file for each of: pulse rate (display as “heart rate” in the output), systolic blood pressure, and diastolic blood pressure. Use pre-infusion values only.
 
Include planned infusions (in the remission induction phase).
 
Statistics and Calculation Methods: Time-points to include are: pre-infusion and 0.25, 0.5, 0.75, 1, 1.5, 2, ... 6 hours post-infusion.
 
Numeric Precision and Formatting of Statistics: See mockup

---	--

Time-point Relative to Infusion Start		Value at Time-point	Change from Pre-infusion
Infusion 1			
Pre-infusion	n	nn	
	Mean (SD)	xxx.x (xx.x)	
	Median	xxx.x	
	Q1 – Q3 (IQR)	xx.x-xx.x(xx.x)	
	Min-Max	xxx.x-xxx.x	
0.25 hours Post	n	nn	nn
	Mean (SD)	xxx.x (xx.x)	xxx.x (xx.x)
	Median	xxx.x	xxx.x
	Q1 – Q3 (IQR)	xx.x-xx.x(xx.x)	xx.x-xx.x(xx.x)
	Min-Max	xxx.x-xxx.x	xxx.x-xxx.x
Infusion 2 ...			

ID: VS002SP
 
Vital Sign Results and Change from Baseline by Visit
	
STREAM Template: VST01
 
Analysis Population: Safety Evaluable Population
 
Column Variables: Value at visit and Change from Baseline.
 
Statistics and Calculation Methods: Analysis visits to include are: Baseline, Weeks 1 to 3, Months 1, 2, 4, 6, 9, 12, 15 and 18.
 
Values at visits to include only patients for whom a baseline value is included.
 
Numeric Precision and Formatting of Statistics: See mockup

--	--

Visit		Value at Visit	Change from Baseline
Day 1 (Baseline)	n	nn	
	Mean (SD)	xxx.x (xx.x)	
	Median	xxx.x	
	Q1 – Q3 (IQR)	xx.x-xx.x(xx.x)	
	Min-Max	xxx.x-xxx.x	
Week 1	n	nn	nn
	Mean (SD)	xxx.x (xx.x)	xxx.x (xx.x)
	Median	xxx.x	xxx.x
	Q1 – Q3 (IQR)	xx.x-xx.x(xx.x)	xx.x-xx.x(xx.x)
	Min-Max	xxx.x-xxx.x	xxx.x-xxx.x
Week 2	n	nn	nn
	Mean (SD)	xxx.x (xx.x)	xxx.x (xx.x)
	Median	xxx.x	xxx.x
	Q1 – Q3 (IQR)	xx.x-xx.x(xx.x)	xx.x-xx.x(xx.x)
	Min-Max	xxx.x-xxx.x	xxx.x-xxx.x
...			

ID: VS003SP Vital Sign Results and Changes from Baseline Above and Below Specified Limits by Visit	STREAM Template: None				
	Analysis Population: Safety Evaluable Population				
	Analysis Variables: Separate tables in one file for each of: pulse rate (display as “heart rate” in the output), systolic blood pressure, and diastolic blood pressure.				
	Statistics and Calculation Methods: Use pre-infusion values only. Analysis visits to include are: Baseline, Weeks 1 to 3, Months 1, 2, 4, 6, 9, 12, 15 and 18. Values at visits to include only patients for whom a baseline value is included.				
Cut-off for each of the vital sign parameters are as follows:					
		Value at Visit		Change from Baseline	
Vital Sign	Units	Low	High	Decrease	Increase
Pulse rate	beats/min	<50	>100	≥20	≥20
Systolic blood pressure	mmHg	≤90	≥140	≥20	≥20
Diastolic blood pressure	mmHg	≤50	≥90	≥15	≥15
As well as by-visit summaries, also summarise the number of patients who are low or high, or have a decrease/increase, at any post-baseline time-point. This will include all post-baseline data included in this analysis. A patient may count at most once towards the count on none, one or more of the 4 categories (see mockup).					
Percentages are based on n.					
Numeric Precision and Formatting of Statistics: See mockup					

[figure not shown]
Visit		Rituximab (N = nnn)
Day 1 (Baseline)	n	nn
	Value at Visit	
	<50	nn (xx.x%)
	≥50 to ≤100	nn (xx.x%)
	>100	nn (xx.x%)
Week 1	n	nn
	Value at Visit	
	<50	nn (xx.x%)
	≥50 to ≤100	nn (xx.x%)
	>100	nn (xx.x%)
	Change from Baseline	
	Decrease ≥20	nn (xx.x%)
	Increase ≥20	nn (xx.x%)
...		
Month 6	n	nn
	Value at Visit	
	<50	nn (xx.x%)
	...	
	Change from Baseline	
	...	
Any Post-baseline Value	n	nn
	Values at Visits	
	<50	nn (xx.x%)
	>100	nn (xx.x%)
	Changes from Baseline	
	Decrease ≥20	nn (xx.x%)
	Increase ≥20	nn (xx.x%)

[figure not shown]
[figure not shown]

ID: VS004SP
 
Listing of Vital Sign Abnormalities
	
STREAM Template: LBL02A* (see mock)
 
Analysis Population: Safety Evaluable Population
 
Numeric Precision and Formatting of Statistics: See mockup Include patients with at least one post-baseline "abnormal" VS test. Flag high (H) and low (L) results.

---	---

[figure not shown]
[figure not shown]
Vital Sign Test (Unit)	Center / Patient ID	Age/Sex	Study Day	Date	Result	Normal Range
<Vital Sign Test> (<unit>)	xxxx/xxx	xx	xx	ddMMYY	xx L	xx-xx
	xxxx/xxx	xx	xx	ddMMYY	xx L	xx-xx
	xxxx/xxx	xx	xx	ddMMYY	xx H	xx-xx
	xxxx/xxx	xx	xx	ddMMYY	xx	xx-xx
	xxxx/xxx	xx	xx	ddMMYY	xx L	xx-xx
	xxxx/xxx	xx	xx	ddMMYY	xx	xx-xx
	xxxx/xxx	xx	xx	ddMMYY	xx H	xx-xx

[figure not shown]
[Redacted]

[figure not shown]

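### VS001SP's pre-infusion-only instruction contradicts the table it specifies, which also omits temperature; secondarily, VS003SP's fixed Low/High counts are neither split by baseline status nor age-referenced

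*SAP*

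**What the plan says.** SAP Section 8 describes the readings at infusion visits. Temperature, pulse and blood pressure are taken just before the infusion, every 15 minutes for an hour, every 30 minutes until the end, and again at least an hour after completion. The section commits to summaries by planned time-point and as change from that visit's pre-infusion reading. It mentions pre-infusion values separately, for the by-visit summary.

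**VS001SP** (Section 8.1) is the table for the infusion readings. Its parameters are pulse, systolic and diastolic pressure, and the list ends "and diastolic blood pressure. Use pre-infusion values only". The same specification asks for time-points from 0.25 to 6 hours, a column for values after infusion and a column for change from pre-infusion. Its mock-up has a 0.25-hour row with both columns filled.

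**VS003SP** counts patients outside set limits. It says "Cut-off for each of the vital sign parameters are as follows" and gives pulse <50 and >100 beats/min, systolic ≤90 and ≥140 mmHg, and diastolic ≤50 and ≥90 mmHg. There are also change limits of 20, 20 and 15. The scope is "Statistics and Calculation Methods: Use pre-infusion values only", and "Values at visits to include only patients for whom a baseline value is included". It then asks the programmer to "summarise the number of patients who are low or high, or have a decrease/increase, at any post-baseline time-point", using all "post-baseline data included in this analysis". The mock-up puts these counts in a block labelled "Any Post-baseline Value".

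**VS004SP** lists abnormal results. It says "Flag high (H) and low (L) results" beside a normal-range column whose source is not named.

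**The concern.** VS001SP is the only output in Section 8.1 specified to summarize vital signs during infusion. An instruction to use pre-infusion values alone removes what the table exists to show. A programmer must either follow it and produce an almost empty table, or override the specification without record. Temperature is lost in either case, because it is not among the parameters.

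In VS003SP, one set of limits serves an age range of 2 to under 18 years (Protocol 4.1.1), and the pooled post-baseline Low/High rows take no account of where a child started. SAP Section 2.1.5 makes vital signs a secondary safety outcome. The counts could therefore be read as new findings on treatment when some reflect a child's usual value or the number of times the child was measured.

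**Working it through.** The plan states no expected rate of vital-sign flags, so there is no figure of its own to reproduce.

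**1. VS001SP against itself**
- Later time-points: 0.25, 0.5 and 0.75 h (3), then 1 to 6 h in half-hour steps (11), so 3 + 11 = 14. The mock-up counts them from the start of infusion.
- Blocks per parameter: 4 planned infusions × (1 pre-infusion + 14 later) = 60.
- With pre-infusion values only, 4 × 1 = 4 of the 60 are filled. A change from pre-infusion needs a later reading, so that column has no entries.
- The title, columns, time-points, mock-up and Section 8 all require later readings. Only the one sentence excludes them.

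**2. Temperature**
- Section 8 includes it in the set measured around each infusion and summarized by time-point. VS001SP lists three parameters and temperature is not one.

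**3. VS003SP and baseline status**
- A child above 100 beats/min on Day 1 and unchanged afterwards enters the any-post-baseline >100 row. Nothing in that row separates this child from one who was below the limit on Day 1.
- Laboratory table LB004SP (SAP 7.4) does make the separation: its post-baseline Low and High rows are divided into Change from Baseline and Sustained.
- The Day 1 row is one visit. The pooled row covers at least Weeks 1–3 (3) and Months 1, 2, 4, 6, 9, 12, 15 and 18 (8), so 3 + 8 = 11 visits. Three-monthly visits continue after Month 18 until closeout, so 11 is a minimum.
- Illustration on assumed values, for repeat measurement only: let each of 25 patients have the same flag probability p at every visit, with no change over time. The expected Day 1 count is 25p. Over 11 independent visits the pooled count is 25 × [1 − (1 − p)^11]. The lower end of each range uses a one-factor normal model with within-patient correlation 0.8.

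| Assumed p | Day 1 | Any of 11 visits (correlation 0.8 to independence) |
|---|---|---|
| 0.05 | 1.25 | 3.9 to 10.8 |
| 0.10 | 2.5 | 6.7 to 17.2 |
| 0.30 | 7.5 | 14.5 to 24.5 |

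For example, 1 − 0.90^11 = 0.686, and 25 × 0.686 = 17.2. The pooled row rises with no change in any patient, so it is not like-for-like with Day 1.

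**4. VS003SP and age**
- The limits carry no age, sex or height term, and SAP Section 3.4 rules out subgroup analyses, so no age breakdown compensates.
- LB004SP uses the ranges held with the laboratory data, and the accompanying listing groups those ranges by age (<12, ≥12) and gender.
- The documents give neither paediatric norms for pulse or blood pressure nor the age mix that will enrol. An age-related flag rate therefore cannot be computed from them, and none is given here.

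**The case against.** The VS001SP error is editorial: every other element of the specification points to one reading, and a competent programmer would probably find it. That lowers the risk but leaves the sentence wrong, and it does not restore temperature.

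On VS003SP, the table is titled by specified limits, not abnormality, and its rows print the numbers themselves. Several stronger readings are tempting and do not stand:

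- A reader might infer that VS003SP has no baseline comparator. It prints a Day 1 row with the same categories, and the any-post-baseline block has Decrease and Increase rows. By-visit rows can be read against Day 1. The defect is the missing split in the pooled Low/High rows.
- A reader might infer that fixed limits break a rule of the plan. The documents follow no single principle. The IgG, neutrophil and platelet limits in Protocol 4.1.2 are fixed, and the height-referenced hypertension item in Protocol Table 2 measures disease activity; it is not a safety limit.
- A reader might expect many false flags in young children. That rests on paediatric means that the documents do not supply. If no enrolled child's usual value lies near a limit, the age effect is nil.
- A reader might see a contradiction between VS003SP's pre-infusion scope and its use of all post-baseline data. The neighbouring LB005SP uses similar wording to mean results not confined to analysis windows. Read that way, the two instructions agree.

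**Conclusion.** VS001SP is wrong as written. Taken literally, it fills 4 of 60 blocks per parameter, leaves the change column empty and summarizes no reading taken during infusion; it also omits temperature. This follows from the text and depends on no assumption.

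VS003SP is a cheap improvement, not an error. Its pooled Low/High rows mix patients already beyond a limit on Day 1 with those newly beyond it, and pool at least 11 visits against one. Its limits are not age-referenced, although the same SAP groups laboratory ranges by age and gender. The repeat-measurement figures above are illustrations on assumed rates. The age effect has no size that the documents can support.

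Severity is low overall. The outputs are descriptive, vital signs are a secondary safety measure, and nothing is tested. VS003SP's change-from-baseline rows, VS002SP and adverse-event reporting are unaffected.

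**What to change.** **VS001SP.** Delete the sentence restricting it to pre-infusion values, and add temperature to the parameters. This costs a one-line edit and one more table in the same file.

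**VS003SP.**
- Split the any-post-baseline Low and High rows by baseline status, as LB004SP does, and keep the change-from-baseline rows. The split separates children already beyond a limit; it does not remove the effect of repeated measurement, which a footnote should state.
- Either use age-referenced pulse categories and age-, sex- and height-referenced blood pressure categories from a named published source, or label the fixed-limit counts as not age-adjusted. The first option needs a lookup table, one stated age rule (for example, age at baseline) and a rule for carrying height forward at Weeks 1–3, where height is not scheduled. The label alone costs almost nothing.

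**Optional clarifications.** State that VS003SP's pooled rows use all pre-infusion values, including those outside analysis windows, and name the source of VS004SP's normal range.

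None of this needs new data; the cost is a little extra programming.
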